5.4.2 Nivolumab

There are no nivolumab dose modifications. Depending on toxicities, nivolumab will either be given at full dose, withheld, or discontinued.

NOTE: Nivolumab treatment may only be held for a maximum of 12 weeks for nivolumab-specific toxicity, otherwise the patient should be removed from all protocol therapy.

Grading of AEs is based on the NCI CTCAE.

If a patient discontinued nivolumab due to nivolumab-specific toxicities, chemotherapy may continue, if appropriate. Patient should be followed for assessment of the toxicities until the AEs resolve or are deemed irreversible.

Rev. Add3

5.4.2.1 Management Algorithms for Nivolumab

Immuno-oncology (I-O) agents are associated with adverse events that can differ in severity and duration than adverse events caused by other therapeutic classes. Nivolumab is considered an immuno-oncology agent in this protocol. Management algorithms have been developed to assist investigators in assessing and managing the following groups of adverse events: Gastrointestinal, Renal, Pulmonary, Hepatic, Endocrinopathies, Skin, and Neurological. See [Appendix III](#) for the treatment algorithms.

Early recognition and intervention are recommended according to the management algorithms found in [Appendix III](#). In addition, the Investigator Brochure (IB, version 16, 2017) includes ophthalmologic evaluations for any visual symptoms in order to evaluate for nivolumab related uveitis. Investigators should follow the algorithms in [Appendix III](#) for immune- related events.

NOTE: The algorithms are essential guides for AE management, but the guidance provided in these algorithms should not replace the investigator's medical judgment but should complement it.

For patients expected who require more than 4 weeks of corticosteroids or other immunosuppressants to manage an adverse event, consider the following recommendations: Antimicrobial/antifungal prophylaxis per institutional guidelines to prevent opportunistic infections such as *Pneumocystis jiroveci* and fungal infections.

Early consultation with an infectious disease specialist should be considered. Depending on the presentation, consultation with a pulmonologist for bronchoscopy or a gastroenterologist for endoscopy may also be appropriate.

In patients who develop recurrent adverse events in the setting of ongoing or prior immunosuppressant use, an opportunistic infection should be considered in the differential diagnosis.

Additional details on the safety of nivolumab, including results from clinical studies, are available in the IB (IB, version 16, 2017).

Please refer to the Nivolumab Investigator Brochure or [Appendix III](#) to the protocol for toxicity management algorithms which include specific treatment guidelines. These algorithms should be followed unless there are specific clinical circumstances for which the treating physician decides an alternative treatment approach is clinically appropriate. Consultation with the study PI is recommended.

In places that there are differences from the algorithms regarding protocol directed drug modifications, please follow the protocol specific guidelines in this section.

Generally we strongly encourage early evaluation while withholding drug, and appropriate treatment as indicated in the management tables and event specific guidelines.

ALL OTHER EVENTS	Management/Next Dose for Nivolumab
≤ Grade 1	No change in dose
Grade 2	Hold until ≤ Grade 1 OR baseline (exceptions as noted below)
Grade 3	Off protocol therapy (exceptions as noted below)
Grade 4	Off protocol therapy
Recommended management: As clinically indicated	

- Any grade 2 drug-related uveitis or eye pain or blurred vision that does not respond to topical therapy and does not improve to Grade 1 severity within the re-treatment period OR requires systemic treatment should go off protocol treatment
- Any adverse event, laboratory abnormality, or intercurrent illness which, in the judgment of the investigator, presents a substantial clinical risk to the subject with continued study drug dosing should go off protocol treatment.
- Any grade 3 or 4 drug-related laboratory abnormality (i.e. amylase, lipase) or electrolyte abnormality, that can be managed with electrolyte replacement,

hormone replacement, insulin or that does not require treatment does not require discontinuation.

Skin Rash and Oral Lesions	Management/Next Dose for Nivolumab
≤ Grade 1	No change in dose *
Grade 2	Hold* until Grade ≤ 1 or resolved. Resume at same dose level.
Grade 3	Hold* until ≤ Grade 1. Resume at same level at investigator discretion
Grade 4	Off protocol therapy

*Patients with purpuric or bullous lesions must be evaluated for vasculitis, Steven-Johnson syndrome, TEN, and autoimmune bullous disease including oral lesions of bullous pemphigus/pemphigoid. Pruritus may occur with or without skin rash and should be treated symptomatically if there is no associated liver or GI toxicity. Note skin rash typically occurs early and may be followed by additional events particularly during steroids tapering.

Recommended management: AE management guidelines

Liver Function AST, ALT, Bilirubin	Management/Next Dose for Nivolumab
≤ Grade 1	No change in dose
Grade 2	Hold until WNL or baseline. Resume at same dose level.
Grade 3	Off protocol therapy
Grade 4	Off protocol therapy

Continued treatment with active immune mediated hepatitis may exacerbate ongoing inflammation. Holding drug to evaluate LFT changes and early treatment are recommended.

LFT changes may occur during steroid taper from other events and may occur together with other GI events including cholecystitis/pancreatitis.

Recommended management: see Hepatic AE management algorithm

Diarrhea/ Colitis	Management/Next Dose for Nivolumab
≤ Grade 1	No change in dose
Grade 2	Hold until baseline. No change in dose
Grade 3	Off protocol therapy.
Grade 4	Off protocol therapy

See GI AE Algorithm for management of symptomatic colitis.

Patients with grade 2 symptoms but normal colonoscopy and biopsies may be retreated after resolution. Evaluation for all patients for additional causes includes *C. diff*, acute and self-limited infectious and foodborne illness, ischemic bowel, diverticulitis, and IBD.

Recommended management: see GI AE management Algorithm

Pneumonitis	Management/Next Dose for Nivolumab
≤ Grade 1	No change in dose
Grade 2	Hold dose pending evaluation. Resume no change in dose after pulmonary and/or ID consultation as needed.
Recurrent Grade 2 or Grade 3	Hold dose pending evaluation. Off protocol therapy.

Pneumonitis	Management/Next Dose for Nivolumab
Grade 4	Off protocol therapy
Distinguishing inflammatory pneumonitis is often a diagnosis of exclusion for patients who do not respond to antibiotics and have no causal organism identified including influenza. Most patients with respiratory failure or hypoxia will be treated with steroids. Bronchoscopy may be required and analysis of lavage fluid for lymphocytic predominance may be helpful. Patients with new lung nodules should be evaluated for sarcoid like granuloma. Please consider recommending seasonal influenza killed vaccine for all patients.	
Recommended management: See Pulmonary Adverse Event Management Algorithm	

Neurologic events	Management/Next Dose for Nivolumab
≤ Grade 1	No change in dose.
Grade 2	Hold dose pending evaluation and observation. Hold until ≤ Grade 1. Off protocol therapy per investigator discretion. Resume at same dose level for peripheral isolated n. VII (Bell's palsy).
Grade 3	Off protocol therapy
Grade 4	Off protocol therapy
Patients with any CNS events including aseptic meningitis, encephalitis, symptomatic hypophysitis, or myopathy, peripheral demyelinating neuropathy, cranial neuropathy (other than peripheral n. VII), Guillain-Barre Syndrome, myasthenia gravis should be off study.	
Recommended management: See Neurologic Adverse Event Management Algorithm	

Renal	Management/Next Dose for Nivolumab
≤ Grade 1	No change in dose
Grade 2	Hold until ≤ Grade 1. Resume at same dose level.
Grade 3	Off protocol therapy.
Grade 4	Off protocol therapy.
Recommended management: See Renal Adverse Event Management Algorithm	

Rev. Add3
Rev. Add4

5.4.2.2 Treatment of Nivolumab-Related Infusion Reactions

Since nivolumab contains only human immunoglobulin protein sequences, it is unlikely to be immunogenic and induce infusion or hypersensitivity reactions. However, if such a reaction were to occur, it might manifest with fever, chills, rigors, headache, rash, urticaria, angioedema, pruritis, arthralgias, hypo- or hypertension, bronchospasm, or other symptoms.

All Grade 3 or 4 infusion reactions should be reported as an SAE if criteria are met. Infusion reactions should be graded according to NCI CTCAE guidelines.

Treatment recommendations are provided below and may be modified based on local treatment standards and guidelines as medically appropriate:

Remain at bedside and monitor subject until recovery from symptoms

For Grade 1 symptoms: (Mild transient reaction; infusion interruption not indicated; intervention not indicated)

If clinically appropriate, infusion rate may be slowed or interrupted and restarted at 50% of the original infusion rate when symptoms resolve; if no further complications ensue after 30 minutes, the rate may be increased to 100% of the original infusion rate. Monitor patient closely.

The following prophylactic premedications are recommended for future infusions: diphenhydramine 50 mg (or equivalent, oral) and/or acetaminophen 325 to 1000 mg at least 30 minutes before additional nivolumab administrations, slowing infusion rate as above.

For Grade 2 symptoms: (Therapy or infusion interruption indicated but responds promptly to symptomatic treatment (e.g., antihistamines, NSAIDS, narcotics, IV fluids); prophylactic medications indicated for \leq 24 hrs), and no further nivolumab administration should be considered at that visit.

Stop the nivolumab infusion, begin an IV infusion of normal saline, and treat the subject with diphenhydramine 50 mg IV (or equivalent, oral) and/or acetaminophen 325 to 1000 mg; remain at bedside and monitor patient until resolution of symptoms. Corticosteroid or bronchodilator therapy may also be administered as appropriate. If it is deemed clinically appropriate to restart, then restart the infusion at 50% of the original infusion rate when symptoms resolve; if no further complications ensue after 30 minutes, the rate may be increased to 100% of the original infusion rate. Monitor patient closely. If symptoms recur, re administer diphenhydramine 50 mg (oral or IV), and remain at bedside and monitor the patient until resolution of symptoms. The amount of study drug infused must be recorded on the electronic case report form (eCRF).

The following prophylactic premedications are recommended for future infusions: diphenhydramine 50 mg (or equivalent, oral) and (acetaminophen) 325 to 1000 mg should be administered at least 30 minutes before additional nivolumab administrations. If necessary, corticosteroids (recommended dose: up to 25 mg of IV hydrocortisone or equivalent) may be used.

For Grade 3 or Grade 4 symptoms: (Severe reaction),
Grade 3 symptoms: prolonged [i.e., not rapidly responsive to symptomatic medication and/or brief interruption of infusion]; recurrence of symptoms following initial improvement; hospitalization indicated for other clinical sequelae [e.g., renal impairment, pulmonary infiltrates]).

Grade 4 symptoms: (life-threatening consequences; urgent intervention indicated).

Nivolumab will be permanently discontinued

Immediately discontinue infusion of nivolumab. Begin an IV infusion of normal saline, and bronchodilators, epinephrine 0.2 to 1 mg of a 1:1,000 solution for subcutaneous administration or 0.1 to 0.25 mg of a 1:10,000 solution injected slowly for IV administration, and/or diphenhydramine 50 mg (oral or IV) with methylprednisolone 100 mg IV (or equivalent), as needed. Patient should be monitored until the investigator is comfortable that the symptoms will not recur.

Investigators should follow their institutional guidelines for the treatment of anaphylaxis. Remain at bedside and monitor patient until recovery from symptoms.

In the case of late-occurring hypersensitivity symptoms (e.g., appearance of a localized or generalized pruritis within 1 week after treatment), symptomatic treatment may be given (e.g., oral antihistamine, or topical or oral corticosteroids). Additional treatment prior to next dose as per guidelines above.

Please note that late occurring events including isolated fever and fatigue may represent the presentation of systemic inflammation. Please evaluate accordingly.

Rev. Add1
Rev. Add3

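### Section 5.4.2.2 both rules out further nivolumab at the visit after a Grade 2 infusion reaction and describes restarting the infusion

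*Combined protocol and SAP*

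**What the plan says.** Section 5.4.2.2 sets out management of nivolumab infusion reactions by grade, under a general introduction: "Treatment recommendations are provided below and may be modified based on local treatment standards and guidelines as medically appropriate".

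The Grade 2 block has three parts:

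- **Opening sentence.** After describing what counts as Grade 2, it ends "and no further nivolumab administration should be considered at that visit".
- **Management paragraph.** It begins "Stop the nivolumab infusion, begin an IV infusion of normal saline, and treat the subject with diphenhydramine 50 mg IV". It continues "If it is deemed clinically appropriate to restart, then restart the infusion at 50% of the original infusion rate when symptoms resolve", followed by "if no further complications ensue after 30 minutes, the rate may be increased to 100% of the original infusion rate. Monitor patient closely". For recurrence it says "If symptoms recur, re administer diphenhydramine 50 mg (oral or IV), and remain at bedside and monitor the patient until resolution of symptoms". It closes by requiring the amount of drug infused to be entered on the eCRF.
- **Later infusions.** A separate paragraph begins "The following prophylactic premedications are recommended for future infusions: diphenhydramine 50 mg (or equivalent, oral) and (acetaminophen) 325 to 1000 mg should be administered".

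The Grade 3 or 4 block comes next and calls for permanent discontinuation of nivolumab.

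**The concern.** The opening sentence says further nivolumab is not to be considered at the visit. The management paragraph asks the site to consider exactly that, and supplies a restart rate, a step-up and a plan for recurrence. A site that uses the restart option departs from the opening sentence. A site that treats the opening sentence as binding must ignore much of the paragraph below it.

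Three things are at stake:

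- **Safety.** The question is whether to re-expose a patient who has just reacted to the investigational drug. The answer should not depend on which sentence a site reads as controlling.
- **Exposure.** Whether an Arm A patient receives a partial or a completed dose at that visit would depend on the site's reading.
- **Oversight.** Monitors and auditors have no clear standard for saying which action departs from the protocol.

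**Working it through.** No calculation decides this point; it is a comparison of text. The arithmetic at the end only bounds its size.

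**1. Same grade?** Yes. Both instructions fall after the Grade 2 heading and before the Grade 3 or 4 heading, in consecutive paragraphs.

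**2. Same visit?** Yes. The paragraph describes stopping an infusion in progress, treating at the bedside, restarting when symptoms resolve and reassessing after 30 minutes. Later infusions have their own paragraph, so the restart cannot be read as meaning the next visit.

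**3. Is either instruction limited so that they do not overlap?** No. The bar is not confined to reactions that fail to resolve or that recur. The restart depends on clinical judgement, but weighing a restart is what the bar rules out.

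**4. Does any other text settle it?** No.

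- The introduction to Section 5.4.2.2 lets sites adapt the recommendations to local standards, but does not say what the default is.
- Section 5.4.2.1 says the protocol section prevails where it differs from the management algorithms. Here both instructions are in the protocol section.
- The Appendix III algorithms cover endocrine, gastrointestinal, hepatic, neurological, pulmonary, renal and skin events, not infusion reactions.

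**5. What follows if a site does restart?** If symptoms recur, the Grade 2 text says to re-treat and monitor, but not whether nivolumab continues. The Grade 3 description in the same section includes symptoms that come back after first improving, and Grade 3 means permanent discontinuation. Section 5.2.8 also attaches expedited reporting to infusion reactions of Grade 3 or higher. Recurrence after a restart therefore falls under two grades with different consequences.

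**6. How many patients?**

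- Arm A: 150 randomized equally, 150 / 2 = 75.
- Cited rate: Section 1.2.1.4 reports infusion-related reactions in 3% of nivolumab patients, none Grade 3–4, in the phase 3 trial in non-squamous NSCLC. 75 × 0.03 = 2.25, about 2 patients.
- Ceiling: the risk table in Section 5.3 lists the event in the column headed at most 20%. 75 × 0.20 = 15 patients.
- Both percentages include Grade 1, so on either assumption the Grade 2 count is no higher.

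**7. How many infusions per patient?** The cap is 50 doses (Sections 5.1 and 5.6). This matches the schedule over 104 weeks: 4 doses in the first 12 weeks, then (104 − 12) / 2 = 46, and 4 + 46 = 50. A patient treated to the 8-month median PFS assumed in Section 9.4 is on treatment for about 8 × 52.18 / 12 = 34.8 weeks. That gives 4 + (34.8 − 12) / 2 = 4 + 11.4, or about 15 infusions. These counts describe how often the situation can arise. They should not be multiplied by the percentages above, which are per patient.

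**The case against.** The strongest reply is that these are recommendations, expressly open to local adaptation, and that the restart is permitted rather than required. A site that never restarts complies in practice with both sentences. Both readings stop the infusion, treat the patient and keep bedside monitoring, and the Grade 3 or 4 rule on discontinuation is stated separately. The eCRF entry makes partial doses visible in the data, and the primary PFS analysis of eligible and treated patients does not depend on completing a particular infusion. The numbers are small: 3% comes from monotherapy in another disease, 20% is a column heading rather than an estimate, and 50 infusions is a maximum.

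Much of this stands. The advisory wording weakens any claim that a given action is a protocol deviation. The figures are limits, not forecasts. The primary analysis is untouched.

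It does not remove the contradiction. That one course of action happens to satisfy both sentences does not make them consistent: one says a restart is not to be considered, and the other tells the site how to decide on it and carry it out. Permission to vary a recommendation presupposes that the reader can tell what is recommended. Recording the amount infused documents the resulting variation; it does not say what should have been done.

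**Conclusion.** The concern holds. Two consecutive paragraphs of current protocol text give incompatible guidance for the same Grade 2 reaction at the same visit, and no other provision says which governs.

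The number of patients affected is probably small: about 2 of 75 in Arm A at the one cited rate, and no more than 15 at the ceiling of the risk-table column. Both figures assume 75 treated patients in Arm A and count all grades. The Grade 2 share is not given, and neither figure is specific to nivolumab given with platinum and etoposide. No alpha, power, sample-size or event-count figure changes.

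The point still has to be fixed, because of the kind of instruction involved rather than the count. It concerns re-exposure to the investigational drug after a reaction, and on recurrence it reaches grading, permanent discontinuation and expedited reporting. This review takes no view on which instruction is clinically right.

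**What to change.** Reconcile the opening Grade 2 sentence with the management paragraph in Section 5.4.2.2, so that a single instruction governs the rest of that visit. The medical team decides which. Then bring two dependent sentences into line with the choice:

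- the sentence on recurrence, so that it is consistent with the Grade 3 description in the same section;
- the sentence on recording the amount infused.

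The cost is a short protocol amendment, essentially one sentence plus these alignments, and a notice to sites. The statistical section needs no change.

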5.5 Supportive Care

All supportive measures consistent with optimal patient care will be given throughout the study. Supportive care (including IVF hydration) is not considered non-protocol therapy

The clinical tolerance of the patients, the overall tumor response, and the medical judgment of the investigator will determine if it is in the patient's best interest to continue or discontinue treatment. If treatment is discontinued due to any toxicity, the patient must be followed to monitor duration of toxicity, response and time to progression (even if non-protocol therapy is initiated). Suggested supportive care medications may be substituted at the discretion of the investigator based on drug availability.

Hyperalimentation may be used, but details must be clearly outlined on treatment forms.

Concomitant aminoglycoside antibiotic use should be avoided during cisplatin therapy until patient has fully recovered (i.e., at least 4 weeks from last dose of cisplatin).

The use of bisphosphonates or denosumab is allowed for patients with bone metastasis or hypercalcemia.

Systemic treatment with either corticosteroids (> 10 mg daily prednisone equivalent) or other immunosuppressive medications are prohibited. Topical, ocular, intra-articular, intranasal, and inhalational corticosteroids (with minimal systemic absorption) and adrenal replacement steroid doses > 10 mg daily prednisone are permitted. A brief (less than 3 weeks) course of corticosteroids for prophylaxis (eg, contrast dye allergy) or for treatment of non-autoimmune

conditions (eg, delayed-type hypersensitivity reaction caused by a contact allergen) or prevention of nausea/vomiting is permitted.

The use of erythropoiesis-stimulating agents (ESAs) is allowed if clinically indicated based on the recommendations by the American Society of Clinical Oncology (2010). For patients undergoing myelosuppressive chemotherapy who have a hemoglobin (Hb) level less than 10 g/dL, the ASCO Guideline Update Committee recommends that clinicians discuss potential harms (e.g., thromboembolism, shorter survival) and benefits (e.g., decreased transfusions) of ESAs and compare these with potential harms (e.g., serious infections, immune-mediated adverse reactions) and benefits (e.g. rapid Hb improvement) of RBC transfusions. If used, ESAs should be administered at the lowest dose possible and should increase Hb to the lowest concentration possible to avoid transfusions. Available evidence does not identify Hb levels of 10 g/dL either as thresholds for initiating treatment or as targets for ESA therapy. Starting doses and dose modifications after response or nonresponse should follow US Food and Drug Administration- approved labeling. ESAs should be discontinued after 6 to 8 weeks in nonresponders. ESAs should be avoided in patients with cancer not receiving concurrent chemotherapy, except for those with lower risk myelodysplastic syndromes.

G-CSF and pegylated G-CSF should be used in accordance with American Society of Clinical Oncology (ASCO) and NCCN guidelines. G-CSF and pegylated G-CSF may be used during all treatment cycles for patients for cycle 2 and beyond as indicated. These agents (G-CSF and pegylated G- CSF) may be used at the discretion of the investigator after neutropenia is documented, or prophylactically to reduce the chance of febrile neutropenia at all other times during the study. Growth factor use or dose reduction is only mandated, however, in the setting of prior febrile neutropenia.

The ASCO guidelines state, “even if febrile neutropenia has not occurred, the use of CSFs may be considered if prolonged neutropenia is causing excessive dose reduction or delay in chemotherapy. However, in the absence of clinical data supporting the maintenance of chemotherapy dose intensity, physicians should consider chemotherapy dose reduction as an alternative to the use of CSFs. There are inadequate data to know whether patients with neutropenia but no fever will benefit clinically from the initiation of a CSF at the time neutropenia is diagnosed; intervention with a CSF in afebrile neutropenic patients is not recommended. For the majority of patients with febrile neutropenia, the available data does not support the routine initiation of CSFs as adjuncts to antibiotic therapy. However, certain febrile neutropenic patients may have prognostic factors that are predictive of clinical deterioration, such as pneumonia, hypotension, multiorgan dysfunction (sepsis syndrome), or fungal infection. The use of CSFs together with antibiotics may be reasonable in such high risk patients, even though the benefits of administration under these circumstances have not been definitively proved (ASCO, 2013).”

Diarrhea may occur on either arm. Appropriate supportive measures including Imodium and/or Lomotil should be implemented immediately to prevent dehydration.

Hydration guidelines may be modified at the discretion of the treating physician provided adequate pre and post cisplatin hydration is achieved and renal function remains adequate. One suggested regimen consists of administering cisplatin in

250 cc to 1000 cc of IV fluids following adequate hydration and the establishment of adequate urinary output. It is suggested the pre-cisplatin hydration consist of NS at 500 cc/hr x 1 liter and post-cisplatin hydration consist of 1/2 NS + 10 meq KCl/liter + 1 gram magnesium sulfate/liter + 25 grams mannitol/liter at 500 cc/hr for at least one hour, followed by additional hydration at the discretion of the investigator.

Antiemetic therapy is critical for proper administration of cisplatin/carboplatin. The specific antiemetic regimen is at the discretion of the treating physician, provided adequate control is achieved. However, on the day of cisplatin therapy the investigator should use a steroid medication, a 5HT3 antagonist and NK1 antagonist such as fosaprepitant or aprepitant since cisplatin is highly emetogenic. One such regimen consists of 10 mg of dexamethasone and a high dose of a 5HT3 antagonist (such as 2 mg oral or 10 mcg/kg IV granisetron or 24 mg ondansetron or equivalent) and continuing with 4 days of dexamethasone or equivalent steroid and 4 days of scheduled anti-emetic such as a 5HT3 antagonist. If this regimen is ineffective, consideration of the long-acting 5HT3 antagonist palonosetron should be considered at the discretion of the investigator.

NOTE: Aprepitant should be used with caution in patients receiving concomitant medicinal products, including chemotherapy agents that are primarily metabolized through CYP3A4. Inhibition of CYP3A4 by aprepitant could result in elevated plasma concentrations of these concomitant medicinal products. The effect of aprepitant on the pharmacokinetics of orally administered CYP3A4 substrates is expected to be greater than the effect of aprepitant on the pharmacokinetics of intravenously administered CYP3A4 substrates.

Dexamethasone dose should be reduced by 50% when administered with aprepitant.

Patients are ineligible if administration of a live, attenuated vaccine within 4 weeks before randomization.

